8.7. Adjustment of Dose and/or Treatment Schedule

An adjustment to the dose frequency from weekly to every 2 weeks or a weekly dose reduction may be permitted for safety or efficacy reasons in consultation with the Sponsor Medical Monitor or designee.

8.8. Discontinuation of Study Drug

A patient must permanently discontinue study treatment for any of the following:

- The patient becomes pregnant. Report the pregnancy according to instructions in Section 9.5.4
- The patient withdraws consent
- The patient experiences an AE that necessitates permanent discontinuation of Study Drug
- The patient develops laboratory test abnormalities that meet any of the stopping rules listed in Sections 8.6.1 to 8.6.3
- The patient experiences an AE that necessitates unblinding of the Investigator

The reason for discontinuation of Study Drug must be recorded in the electronic Case Report Form (eCRF) and source documentation.

Patients who early terminate from treatment will complete the Post-Treatment study procedures per the Appendix A.

For patients withdrawn for reasons other than withdrawal of consent every effort should be made to complete the early termination of study procedures and observations at the time of withdrawal (see Appendix A) and ideally within 2 weeks from the last dose of Study Drug.

8.9. Withdrawal of Patients from the Study Procedures

Patients must be withdrawn from study procedures for any of the following:

- Withdrawal of consent
- The patient is unwilling or unable to comply with the protocol

Other reasons for withdrawal of patients from study procedures might include:

- At the discretion of the Investigator for medical reasons
- At the discretion of the Investigator or Sponsor for noncompliance
- Significant protocol deviation

All efforts will be made to complete and report the observations as thoroughly as possible up to the date of withdrawal. All information, including the reason for withdrawal from study, must be recorded in the eCRF.

Any patient who withdraws consent to participate in the study will be removed from further treatment and study observation immediately upon the date of request. These patients should be

encouraged to complete the early termination study procedures and observations at the time of withdrawal (Appendix A).

For patients withdrawn for reasons other than withdrawal of consent every effort should be made to complete the early termination of study procedures and observations at the time of withdrawal (see Appendix A) and ideally within 2 weeks from the last dose of Study Drug.

8.10. Concomitant Therapy and Procedures

The use of concomitant therapies or procedures defined below must be recorded on the patient's eCRF. Adverse events related to administration of these therapies or procedures must also be documented on the appropriate eCRF.

8.10.1. Concomitant Therapy

A concomitant therapy is any non-protocol specified drug or substance (including over-the-counter medications, herbal medications, and vitamin supplements) administered between Screening and the Post-Treatment Evaluation Period.

Allowed Concomitant Therapy

Any other medications deemed necessary by the Investigator are allowed except those listed in the disallowed concomitant therapy.

COVID-19 vaccines are allowed during study participation. However, because the vaccines are associated with local injection site reactions and constitutional symptoms, the vaccination should NOT be dosed on the same day of Study Drug injection and avoid the same site of any Study Drug injection. If a patient has a reaction from a COVID-19 vaccination, ensure patient recovers prior to administering the next Study Drug injection (even if it incurs a delay).

Disallowed Concomitant Therapy

The following are disallowed concomitant therapies:

- Other medications for the treatment of HTN (e.g., minoxidil, diazoxide, renin inhibitors)
- Medications that may cause hyperkalemia unless on a stable dose at least 1 month prior to the Screening visit
- Use of oral anticoagulants unless stable for 4 weeks prior to the first dose of Study Drug and regular monitoring must be performed, per clinical practice during the study unless the patient is receiving vitamin K agonists. If the patient is receiving vitamin K antagonists (e.g., warfarin) INR should be in therapeutic range, as established by the Investigator, for 4 weeks prior to the first dose
- Chronic administration (defined as > 3 days per week for the duration of the trial) of NSAIDs or COX-2 inhibitors (except aspirin for cardiovascular disease provided the total daily dose does not exceed 325 mg)
- Use of phosphodiesterase 5 inhibitors (e.g., sildenafil, tadalafil, vardenafil, avanafil) within 72 hours prior to any scheduled visit

Changes to the stable regimen of antihypertensives allowed at Screening may result in withdrawal of the patient from the Treatment Period.

8.10.2. Concomitant Procedures

A concomitant procedure is any therapeutic intervention (e.g., surgery/biopsy, physical therapy) or diagnostic assessment (e.g., blood gas measurement, bacterial cultures) performed between Screening and the Post-Treatment Evaluation Period.

8.11. Treatment Compliance

Compliance with treatment dosing is to be monitored and recorded in the eCRF by Study Center staff.

9. SERIOUS AND NON-SERIOUS ADVERSE EVENT REPORTING

9.1. Sponsor Review of Safety Information

Safety information will be collected, reviewed, and evaluated by the Sponsor or designee in accordance with the applicable Ionis and/or designee SOPs throughout the conduct of the clinical trial

9.2. Regulatory Reporting Requirements

The Sponsor or designee is responsible for regulatory submissions and reporting to the Investigators of SAEs including suspected unexpected serious adverse reactions (SUSARs) per the International Conference on Harmonization (ICH) guidelines E2A and ICH GCP. Country-specific regulatory requirements will be followed in accordance with local country regulations and guidelines.

Institutional Review Boards will be notified of any SAE according to applicable regulations.

In addition to the Investigator's assessment of relatedness, the Sponsor or designee will evaluate the available information and perform an independent assessment of all reported SAEs and determine if there is a reasonable possibility that the Study Drug (ISIS 757456 or placebo) is causally related to a reported SAE and, therefore, meets the definition of an SUSAR. While the Sponsor's independent causality assessment may differ from the Investigator's assessment, the country-specific regulatory requirements must be followed for expedited reporting of SUSAR to local regulatory authorities.

Appropriate personnel at the Sponsor or designee will unblind SUSARs for the purpose of regulatory reporting. The Sponsor or designee will submit SUSARs to Regulatory Agencies in blinded or unblinded fashion according to local law. The Sponsor or designee will submit SUSARs to Investigators in a blinded fashion.

For the purpose of regulatory reporting of SUSARs, there are no "expected" AEs in this study population. Investigator's Brochure (provided separately) for expected AEs.

9.3. **Definitions**

9.3.1. Adverse Event

An AE can be any unfavorable and unintended sign (including an abnormal laboratory finding, for example), symptom, or disease temporally associated with the use of medicinal (investigational) product, whether or not the AE is considered related to the medicinal (investigational) product.

An AE can therefore be any of the following:

- Any unfavorable and unintended sign (including an abnormal laboratory finding), symptom, or disease temporally associated with the use of a medicinal product, whether or not considered related to the medicinal product
- Any new disease or exacerbation of an existing disease (a worsening in the character, frequency, or severity of a known condition)
- Recurrence of an intermittent medical condition (e.g., headache) not present at Baseline
- Any deterioration in a laboratory value or other clinical test (e.g., ECG, X-ray) that is associated with symptoms or leads to a change in study treatment or concomitant treatment or discontinuation from Study Drug
- Adverse events that are related to a protocol-mandated intervention, including those that occur prior to assignment of study treatment (e.g., screening invasive procedures such as biopsies).

9.3.2. Adverse Drug Reaction and Suspected Unexpected Adverse Drug Reaction

Adverse Drug Reaction (ADR)

In the *pre-approval* clinical experience with a new medicinal product or its new usages, particularly as the therapeutic dose(s) may not have been established, ADR is defined as follows:

All noxious and unintended responses to a medicinal product related to any dose should be considered adverse drug reactions.

The phrase "responses to a medicinal product" means that a causal relationship between the medicinal product and the AE has been determined by the Sponsor as at least a reasonable possibility, i.e., the relationship cannot be ruled out.

Suspected Unexpected Adverse Drug Reaction

A suspected unexpected ADR is any ADR, the nature or severity of which is not consistent with the applicable product information, e.g., Investigator's Brochure for an unapproved medicinal (investigational) product.

A suspected adverse reaction implies a lesser degree of certainty about causality than an adverse reaction.

9.3.3. Serious Adverse Event

A SAE is any AE that in the view of either the Investigator or Sponsor, meets any of the following criteria:

- Results in death
- Is life threatening: that is, poses an immediate risk of death at the time of the event An AE or suspected adverse reaction is considered "life-threatening" if, in the view of either the Investigator or Sponsor, its occurrence places the patient at immediate risk of death. It does not include an AE or suspected adverse reaction that, had it occurred in a more severe form, might have caused death
- Requires inpatient hospitalization or prolongation of existing hospitalization
- Hospitalization is defined as an admission of greater than 24 hours to a medical facility and does not always qualify as an AE
- Results in a persistent or significant incapacity or substantial disruption of the ability to conduct normal life functions
- Results in a congenital anomaly or birth defect in the offspring of the patient (whether the patient is male or female)
- Important medical events that may not result in death, are not life-threatening, or do not require hospitalization may also be considered serious when, based upon appropriate medical judgment, they may jeopardize the patient and may require medical or surgical intervention to prevent one of the outcomes listed in this definition. Examples of such medical events include allergic bronchospasm requiring intensive treatment in an emergency room or at home, blood dyscrasias or convulsions that do not result in inpatient hospitalization, or the development of drug dependency or drug abuse

The terms "severe" and "serious" are not synonymous. Severity refers to the intensity of an AE (e.g., rated as mild, moderate, or severe, or according to National Cancer Institute Common Terminology Criteria for Adverse Events [NCI CTCAE]; the event itself may be of relatively minor medical significance (such as severe headache without any further findings).

Severity and seriousness need to be independently assessed for each AE recorded on the eCRF.

9.3.4. Adverse Event of Special Interest

Adverse events of special interest (AESI), including both serious or non-serious events, is one of scientific and medical concern specific to the Sponsor's product or program, for which ongoing monitoring and rapid communication by the Investigator to the Sponsor could be appropriate.

For the purpose of this study, severe reductions in platelet count $< 50,000/\text{mm}^3$ accompanied by an MB event or CRNMB event, or platelet count of $< 25,000/\text{mm}^3$ independent of an MB or CRNMB event are considered as AEs of special interest. AESI must be reported to the Sponsor within 24 hours to ensure timely submission as the 15-day expedited report by the Sponsor to regulatory agencies.

Adverse events of special interest are required to be reported by the Investigator to the Sponsor immediately, no more than 24 hours of the Investigator's first knowledge of the event for expedited reporting to Regulatory Authorities.

9.4. Monitoring and Recording Adverse Events

Any pre-existing conditions or signs and/or symptoms present in a patient prior to the start of the study (i.e., before informed consent) should be recorded as Medical History and not recorded as AEs unless the pre-existing condition worsened. The Investigator should always group signs and symptoms into a single term that constitutes a **single unifying diagnosis** if possible. Before a diagnosis is confirmed, all symptoms should be reported as separate AEs.

9.4.1. Serious Adverse Events

In the interest of patient safety, and in order to fulfill regulatory requirements, all SAEs (regardless of their relationship to Study Drug) should be reported to the Sponsor or designee within 24 hours of the Study Center's first knowledge of the event. The collection of SAEs will begin after the patient signs the informed consent form and stop at the end of the patient's Follow-up Period which is defined as Study Day 169. When the Investigator is reporting by telephone, it is important to speak to someone in person versus leaving a message.

Once the patient is randomized to study drug, SAEs should be reported using electronic SAE electronic data capture system (EDC) whenever possible. In situations where electronic SAE submission is unavailable or of an SAE occurs prior to the patient's randomization, a **paper** Serious Adverse Event Form should be completed, and a copy should be faxed or emailed to the Sponsor or designee. For SAEs reported after randomization, information submitted on paper form should be entered into EDC as soon as the system becomes available. The SAE reporting instruction, including the fax number and email address can be found in the Investigator site file for the study.

Detailed follow-up information should be actively sought and promptly submitted electronically or on a Serious Adverse Event Form if reporting by paper before randomization.

All SAEs will be followed until resolution. Serious Adverse Events that remain ongoing past the patient's last protocol-specified follow-up visit will be evaluated by the Investigator and Sponsor. If the Investigator and Sponsor agree the patient's condition is unlikely to resolve, the Investigator and Sponsor will determine the follow-up requirement.

9.4.2. Non-Serious Adverse Events

The recording of non-serious AEs will begin after the patient signs the informed consent form and will stop at the end of the patient's Follow-up Period, which is defined as Study Day 169. The Investigator will monitor each patient closely and record all observed or volunteered AEs on the Adverse Event Case Report Form.

9.4.3. Evaluation of Adverse Events (Serious and Non-Serious)

The Investigator's opinion of the following should be documented on the Adverse Event Case Report Form.

9.4.3.1. Relationship to the Study Drug

The event's relationship to the Study Drug (ISIS 757456 or placebo) is characterized by one of the following:

- **Related:** There is clear evidence that the event is related to the use of Study Drug, e.g., confirmation by positive re-challenge test
- **Possible:** The event cannot be explained by the patient's medical condition, concomitant therapy, or other causes, and there is a plausible temporal relationship between the event and Study Drug (ISIS 757456 or placebo) administration
- Unlikely/Remote: An event for which an alternative explanation is more likely (e.g., concomitant medications or ongoing medical conditions) or the temporal relationship to Study Drug (ISIS 757456 or placebo) administration and/or exposure suggests that a causal relationship is unlikely (For reporting purposes, Unlikely/Remote will be grouped together with Not Related)
- **Not Related:** The event can be readily explained by the patient's underlying medical condition, concomitant therapy, or other causes, and therefore, the Investigator believes no relationship exists between the event and Study Drug

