2.5.2. Risk Assessment

The known potential risks to study participants associated with ISIS 757456 are elaborated on in the Guidance for the Investigator section of the Investigator's Brochure. Additional study associated risks are:

Table 1: Known Risks Associated with RAAS Blockade

Potential Risk of Clinical Significance	Summary of Data/Rationale for Risk	Mitigation Strategy
Hypotension	RAAS blockade may lower BP Duration of effect: Long half-life of the ASO Extent of effect: AGT is the most upstream molecule in RAAS pathway	Eligibility criteria exclude patients at enhanced risk and Weekly BP monitoring Monitoring and stopping rules in place for hypotension
Hyperkalemia	RAAS blockade is known to increase serum potassium	ISIS 757456 is expected to have less effect on the renal RAAS system (less elevation of serum potassium) than ACEi, ARB or direct renin antagonists Most likely to occur in patients with high serum potassium. Eligibility criteria excludes K+>5.1 mmol/L and patients on medications that may cause hyperkalemia unless on a stable dose at least 1 month prior to the Screening visit and no known history of hyperkalemia per Investigator judgement. Eligibility criteria exclude patients at enhanced risk Monitoring and stopping rules in place for hyperkalemia
ARF	RAAS blockade is known to cause ARF	Based on liver (hepatocyte) targeting via the GalNAc conjugation, ISIS 757456 is expected to have less effect on the renal RAAS system than ACEi, ARB or direct renin antagonists Monitor renal function closely

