8.5.4. Safety Monitoring for Potassium

In the event of a potassium measurement > 5.3 mmol/L at any time during the study (Treatment or Post-Treatment Period), the initial measurement(s) should be confirmed. If the initial potassium measurement is confirmed to be > 5.3 mmol/L, weekly monitoring will be initiated until levels return to < 5.3 mmol/L.

In the event of a potassium measurement ≥ 5.5 mmol/L, but less than 6.0 mmol/L, study drug is to be held. In the event of a potassium measurement ≥ 6.0 mmol/L refer to Section 8.6.5 Stopping Rule for Potassium. In the event of a potassium measurement ≥ 5.5 mmol/L, the Investigator or designee should assess for symptoms consistent with hyperkalemia (e.g., muscle weakness or paralysis). An ECG may be considered per Investigator judgement to assess electrocardiographic signs of hyperkalemia (delayed conduction, heart block, arrhythmias) which, if conducted, should be discussed with the Sponsor Medical Monitor or designee to determine continued dosing with Study Drug. The investigator or designee should consider treating the patients with therapies that reduce the serum potassium, such as a low-potassium diet, diuretics, or a reduction or cessation of medications that can increase the serum potassium (ACEi/ARB). Serum potassium should be measured frequently until documented to be < 5.5 mmol/L. Dosing with Study Drug may continue after a confirmed potassium measurement < 5.5 mmol/L with Investigator and Sponsor Medical Monitor or designee consultation.

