3.7.2. Adverse Events

The number and incidence of adverse events (AEs) will be summarized by Medical Dictionary for Regulatory Activities (MedDRA) version 24.0 preferred term (PT) and system organ class (SOC) for:

Any treatment emergent adverse events (TEAEs).

Serious TEAEs (Treatment-emergent SAEs).

Related TEAEs and SAEs. Related is defined as "Related", "Possible", or missing relationship to study drug.

Any TEAEs by severity. At each severity level of subject summarization, a subject is classified according to the highest severity if the subject reported one or more events. AEs with missing severity will be categorized as "Missing" for this summary.

TEAEs leading to permanent study drug discontinuation.

Serious and non-serious AEs that lead to study discontinuation or investigational drug discontinuation will be listed separately. Non-treatment emergent adverse event will be included and be noted in the subject AE listing.

TEAEs will be defined as those adverse events that either start or worsen in severity on or after the date/time of first dose of study treatment.

In addition, if severity of an AE changes during the study, a separate AE will be recorded for each severity on the AE CRF. "first" and "second" AE will be identify based on AE start date. AE start date of the second record is AE stop date of first record. These linked events will be identified based on "Formlink" dataset and compared pairwise, and consider two cases, where the AE severity (mild/moderate/severe) are compared between the two records in the pair.

Case 1: The first AE record in the pair occurs before first dosing, and the second AE record occurs after first dosing.

If the AE severity or seriousness of the second record is worse than that of the first record, then only the second AE is deemed as a TEAE. Otherwise, neither record is considered as TEAE.

Case 2: Both AE records in the pair occur after first dosing.

Only the worst AE will be deemed as one TEAE.

All TEAEs identified based on the rules above will be summarized in the event number analysis.

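### The Possible causality grade excludes any event that another cause could explain, so a plausibly timed event with a comparably likely alternative fits no grade and may be missed in the related-AE tables

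*Combined protocol and SAP*

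**What the plan says.** Under protocol 9.4.3 the Investigator does the grading: "The Investigator's opinion of the following should be documented on the Adverse Event Case Report Form". Section 9.4.3.1 then forces a single choice, since the relationship "is characterized by one of the following". The four grades are:

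- **Related** demands firm proof of a drug cause, for instance recurrence when the drug is given again.
- **Possible** joins two conditions: "The event cannot be explained by the patient's medical condition, concomitant therapy, or other causes, and there is a plausible temporal relationship".
- **Unlikely/Remote**: another explanation is more likely, or the timing or exposure makes a causal link improbable. For reporting it is merged with Not Related.
- **Not Related**: disease, other treatment or another cause readily accounts for the event, and the Investigator concludes that there is no relationship.

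Protocol 9.3.2 defines an adverse drug reaction by a causal relationship that is "determined by the Sponsor as at least a reasonable possibility, i.e., the relationship cannot be ruled out". Protocol 9.2 adds an independent Sponsor causality assessment, stated for SAEs.

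SAP 3.7.2 builds its related-TEAE and related-SAE tables on the 9.4.3.1 labels: "Related is defined as 'Related', 'Possible', or missing relationship to study drug". Protocol 10.6.2 promises a summary of events potentially related to Study Drug.

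**The concern.** Possible is the grade that should hold events where the drug is a credible cause but not the only one. Here it is reserved for events that nothing else can explain, and the next grade down applies only when something else explains the event better or the timing is against the drug. The ground between the two has no grade.

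This trial will produce events on that ground. Inclusion Criterion 6 requires at least 3 antihypertensives, maintained throughout, so concomitant therapy is always a candidate explanation for hypotension. Protocol 2.2 says that combining agents acting on the renin-angiotensin pathway has been complicated by hyperkalaemia, hypotension and acute renal failure. Table 1 in 2.5.2 lists the same three as risks of the study drug's mechanism, noting for potassium that "RAAS blockade is known to increase serum potassium". Section 8.5.4 names ACEi/ARB among drugs that can raise potassium. Potassium-sparing diuretics are permitted, and only an eGFR below 30 mL/min/1.73 m² is excluded.

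At stake is whether the related-AE tables show what a reader will take them to show: events for which the drug remained a credible cause.

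**Working it through.** No arithmetic applies. The documents give no related-AE rate and no expected number of such events. The check is to take one test event through each definition and then into the SAP table.

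**Test event.** A non-serious TEAE with plausible timing, for which the Investigator considers Study Drug and background therapy (or existing renal disease) about equally likely.

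| Grade (9.4.3.1) | Condition | Met? |
|---|---|---|
| Related | Clear evidence, such as positive re-challenge | No |
| Possible | No other explanation **and** plausible timing | No: timing is met, the first condition is not |
| Unlikely/Remote | Alternative more likely **or** timing/exposure against | No: the alternative is only as likely, and timing is favourable |
| Not Related | Readily explained elsewhere **and** no relationship believed to exist | No: the Investigator holds the drug equally likely |

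The event meets none of the four definitions, yet one must be chosen.

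**Into the SAP table.** The result depends on how the site resolves the gap:

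1. Possible, by departing from the literal text: counted as related.
2. Unlikely/Remote or Not Related: not counted.
3. Left blank: counted, because SAP 3.7.2 treats a missing grade as related.

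The same clinical picture can therefore be inside or outside the related tables for reasons unconnected with the event.

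**Against 9.3.2.** Under that standard the test event qualifies, because a relationship cannot be excluded. The standard is applied by the Sponsor, and the Sponsor review in 9.2 is stated for SAEs. A non-serious event has no second causality assessment described for it.

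**Which events are exposed.**

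- *Hypotension*: every patient, since all take at least 3 blood-pressure-lowering drugs.
- *Hyperkalaemia and renal events*: mainly patients on an ACEi/ARB or potassium-sparing diuretic, or with reduced eGFR. ACEi/ARB is one of seven listed categories in Inclusion Criterion 6, and no text makes it compulsory for each patient. The size of this subset is not given.

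**Which displays are untouched.** None of these filters on relatedness: the all-TEAE, severity and discontinuation tables and the hypotension and hyperkalaemia summary (SAP 3.7.2), and the potassium, eGFR-decline and UPCR categories (SAP 3.7.3).

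**The case against.** The strongest reply has four parts.

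*Being on a drug is not the same as the event being explained by it.* Patients enter on a regimen stable for at least 1 month, with systolic pressure above 130 mmHg at two screening visits, potassium no higher than 5.1 mmol/L and no borderline orthostatic hypotension. An Investigator may reasonably judge that an unchanged regimen does not explain a new event after dosing, and grade it Possible. This stands. A reader might infer that such events default to not related, or that none on active drug could ever be graded Possible. The documents do not support either inference: the lower grades have conditions of their own, which the test event fails.

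*The competing explanation is not universal.* A reader might infer that all of the roughly 150 patients carry a mandatory alternative cause for all three named risks. That is supported for hypotension only.

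*Sections 9.3.2 and 9.4.3.1 have different assessors.* The first is a Sponsor determination and the second an Investigator opinion, and 9.2 foresees that they may differ. So this is an inconsistency of standard rather than two rules imposed on one assessor. It remains relevant, because the SAP tables use the Investigator's grades and no Sponsor assessment is described for non-serious events.

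*The harms are displayed elsewhere.* This also stands. A reader might infer that the trial could miss these harms. It would not: their incidence is shown against randomised placebo without a causality filter, and the potassium and renal stopping rules (8.6.5, 8.6.2) are triggered by laboratory values, not by attribution.

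**Conclusion.** The wording defect is real and its reach is narrow. Read literally, 9.4.3.1 has no grade for a plausibly timed event with a comparably likely alternative, and such an event cannot properly be called Possible. That is out of step with 9.3.2. The related-TEAE/SAE tables inherit the gap, and their content will depend partly on how each site deals with it.

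The effect is confined to those tables. Its size cannot be estimated: of m such events, anywhere from 0 to m could be graded Possible, and the documents give neither m nor any indication of how Investigators will read the definition. The conclusion rests on two assumptions: that the definitions are applied as written, and that no separate grading guidance relaxes them. None appears in the protocol or SAP.

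**What to change.** In 9.4.3.1, redefine Possible as a plausible temporal relationship where a causal role of Study Drug cannot be ruled out, even if medical condition, concomitant therapy or other causes could also explain the event. Keep Unlikely/Remote for events with a more likely alternative or unfavourable timing. Carry the same wording into the CRF completion guidance. The SAP's definition of related can stay, since it takes its labels from 9.4.3.1.

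Apply one standard to every AE. If events already graded are to be revisited, re-grade all of them before unblinding. Re-grading only hypotension, hyperkalaemia and renal events would put two causality standards into one table. If full re-grading is not practical, leave past grades alone and state in the study report when the definition changed.

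The cost is one sentence of protocol text, matching guidance and, if chosen, a blinded re-grade whose workload depends on the number of AEs already recorded. The downside is that more AEs will be graded related in all arms, including placebo. The table should therefore be read as a comparison between arms, not as a count of drug-caused events.
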